13.1.5 Prediction Models

Aims 1 through 3 pertain to the effectiveness of the OUD-CDS intervention relative to UC, predicting that it will increase diagnosis, naloxone prescribing, and access to MOUD, and decrease ED visits and inpatient stays. These hypotheses will be tested using generalized linear mixed models to account for clustering of outcomes within eligible patients and randomized clinics, or using generalized estimating equations to compare event rates. Outcomes will be normalized via distribution-appropriate link functions (e.g., logistic-Normal, Poisson-Normal).

Clinic-randomized treatment group, care system and other predictors will be treated as fixed effects.

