13.2.2.1 Statistical Power

A preliminary power analysis was conducted to estimate the minimum detectable difference in the likelihood of OUD diagnosis (H1.1), naloxone rescue kit order (H1.2) and MOUD order or referral for treatment (H2.2) within 30 days of the index visit, and the number of days covered by a MOUD prescription in the 90 days post-index (H2.2) among patients cared for in OUD-CDS relative to UC clinics (see **Section 13.4**). The power analysis relied on conservative assumptions regarding the numbers of randomized clinics (10, 30, 50) and of eligible patients (50 or 100 per clinic); a range of clinic intraclass correlations consistent with those observed for other process measures at HealthPartners (i.e., $ICC_{clin} = 0.01, 0.03, 0.05$); and central tendency estimates for the outcomes (2%, 5%, 10% and 20% or 70, 50, 30 days not covered in UC). Power estimates will be updated after Sites 2 and 3 are selected and preliminary data to inform analysis assumptions become available.

Effect size estimates for the binary outcomes were calculated using the NIH group randomized trial sample size calculator.[48] The difference in days covered was estimated using the Poisson regression module of PASS 11 software[49] after calculating an effective sample size (i.e., $N_{eff} = (n \text{ clinics} * m \text{ patients per clinic}) / (1 + (m-1) * ICC_{clin})$). In addition, the Poisson model power analysis was conducted to estimate the minimally detectable decrease in days NOT covered in the 90 days to post-index among OUD-CDS relative to UC patients to ensure that the estimated days in both groups remained between 0 and 90 days.

Table 3 summarizes the minimum detectable increases in outcome rates among OUD-CDS relative to UC patients given the aforementioned assumptions. Assuming 30 randomized clinics with 50 high risk patients each, that 5% of UC patients have an OUD diagnosis within 30 days of their index visit and $ICC_{clin} = 0.03$, the H1.1 analysis would be powered (power=0.80, $\alpha_2 = 0.05$) to detect a difference if $\geq 11.35\%$ (odds ratio = 2.43) of OUD-CDS patients have an OUD diagnosis within 30 days of their index visit. For an event occurring among 10% of UC patients given the

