13.3 Statistical Methods for Primary and Secondary Outcomes

This section provides an overview of the statistical methods to be employed in testing the primary and secondary outcomes. A more detailed description of the analysis may be found in the Statistical Analysis Plan. The Statistical Analysis Plan will provide more clarity about the underlying assumptions and methodological decisions regarding primary outcome analyses, including the extent to which either supplement alters the treatment effect.

Hypotheses for Aims 1 and 2 predict that the OUD-CDS intervention will increase the likelihood that patients at high risk of OUD are diagnosed with OUD (H1.1); and that among those at high risk or diagnosed with OUD it will increase the likelihoods that a naloxone rescue kit is ordered (H1.2) and that MOUD is ordered or the patient is referred to a provider who can order MOUD (H2.1), and the number of days covered by an MOUD prescription (H2.2). The hypotheses from Aims 1 and 2 will be tested using generalized linear mixed models so that the likelihood or counts of outcomes may be accurately estimated among OUD-CDS relative to UC clinics, accounting for the clustering of patients within randomized clinics. Binary outcomes (H1.1, H1.2, H2.1) will be normalized using a logistic-Normal link function, while it is anticipated that the count outcome (H2.2) will be normalized using a Poisson-Normal link function. The model will estimate fixed effects of OUD-CDS, care system and other covariates on outcomes, and random intercepts for clinics and patients (H1.1, H1.2, H2.1) or for clinics (H2.2).

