13.4 Significance Testing

The H1.1, H1.2 and H2.1 outcomes will be assessed 3 times for each patient – at the index visit (0 days), and 30 (for primary outcomes) and 90 days post-index. Outcomes that occur at an index visit will be coded as also having occurred by days 30 and 90. Similarly, outcomes that occur between days 1 and 30 will be coded as having occurred by days 30 and 90; and those occurring

between days 31 and 90 will be coded as having occurred by day 90. We expect that the documented actions that providers take will be overwhelmingly attributable to the index visit. Some actions that providers initiate at the index visit, such as placing a treatment referral order, may not be complete until considerations related to safety or availability are addressed. The primary outcome for H1.1, H1.2 and H2.1 will be assessed at 30 days so that these actions, likely initiated at the index visit, may be completed prior to assessing the outcome. It is possible that outcomes will not be documented for patients who have post-index visits within 90 days at non-participating clinics. We assume that these eventualities will be rare and equally likely across treatment groups.

Because virtually all of the information pertinent to the H1.1, H1.2 and H2.1 outcomes will be captured by the day 30 measure, the primary hypothesis test for these models will compare the likelihood of the day 30 outcome by treatment group. The primary hypothesis test for the H2.2 outcome will compare the likelihood of the day 90 outcome by treatment group. These comparisons will be evaluated using a two-sided test with a Type I error rate of 5%. Comparisons at other time points will aid understanding of how relative differences in OUD-CDS versus UC settings may increase or decrease in the short term. For example, OUD-CDS might initiate a course of provider actions that otherwise would not occur (increase) or merely hasten action that eventually takes place in UC settings (decrease).

The Aim 3 outcomes represent counts of events that accrue over the post-index observation periods. The event rates in OUD-CDS versus UC clinics will be evaluated using a two-sided test with a Type I error rate of 5%.

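### The patient random intercept for H1.1, H1.2 and H2.1 does not fit a carried-forward yes/no outcome: a joint fit of days 0, 30 and 90 with time terms has no finite patient SD, and the odds ratio then depends on the fitting method

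*Combined protocol and SAP*

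**What the plan says.** Section 13.3 sets the model for the three binary primary outcomes: "Binary outcomes (H1.1, H1.2, H2.1) will be normalized using a logistic-Normal link function". The fixed part covers treatment group, care system and other covariates, with no time term named. The same sentence then gives the random part: "and random intercepts for clinics and patients (H1.1, H1.2, H2.1) or for clinics (H2.2". H2.2, which has one value per patient, therefore gets a clinic intercept only. Section 13.1.5 describes the models as "generalized linear mixed models to account for clustering of outcomes within eligible patients and randomized clinics".

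Section 13.4 says the three outcomes are assessed at the index visit, day 30 and day 90. On coding: "Outcomes that occur at an index visit will be coded as also having occurred by days 30 and 90"; later events are carried forward in the same way. On the test: "the primary hypothesis test for these models will compare the likelihood of the day 30 outcome by treatment group". It adds: "Comparisons at other time points will aid understanding of how relative differences in OUD-CDS versus UC settings may increase or decrease".

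The power calculation in section 13.2.2.1 uses one outcome per patient and "a range of clinic intraclass correlations consistent with those observed for other process measures at HealthPartners". It has no patient-level variance.

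The protocol does not say whether the three records enter one model, whether that model has time or treatment-by-time terms, or how it is estimated. Section 13.3 leaves detail to a separate Statistical Analysis Plan, which is not among the documents supplied.

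**The concern.** A patient intercept is meaningful when a patient's repeated responses vary around a personal level. Carry-forward coding removes that variation, because once an outcome is yes it stays yes. Section 13.4 also expects nearly all actions to belong to the index visit, so most patients would be 000 or 111. The data then look like perfect within-patient correlation, which a logistic-normal model can reach only with an infinite patient SD.

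At stake are convergence, the size of the reported odds ratio and, under some approximations, the primary test itself, for three of the four primary outcomes. If nothing fixes the method in advance, the remedy for a failed fit would be chosen after the data are seen.

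**Working it through.** **1. The protocol's own figure.** Inputs from section 13.2.2.1: 30 clinics × 50 patients, ICC 0.03, 5% in usual care (UC), power 0.80, two-sided 0.05. The design effect is 1 + 49 × 0.03 = 2.47, and the effective n per arm is 15 × 50 / 2.47 = 303.6. With t multipliers on 28 df (sum 2.903), solve p − 0.05 = 2.903 × √{[p(1−p) + 0.05 × 0.95] / 303.6}. This gives p = 11.42% (protocol 11.35%). For 10% in UC it gives 18.14% (protocol 18.12%), and with 50 clinics 16.02% (protocol 16.02%). The power basis therefore reproduces as a one-record-per-patient, clinic-ICC-only calculation.

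**2. Why a joint fit has no finite maximum.** Let logit P(yes at day t in arm a) = σ(c_at + z), with z standard normal and σ the patient SD. At any finite σ, impossible patterns such as 010 receive positive probability. As σ grows, the model becomes a threshold rule: yes at day t if z > −c_at. Setting c_at = Φ⁻¹(rate at day t in arm a) then matches all four pattern frequencies in each arm. The bound is approached only as σ → ∞. The conditional day-30 log odds ratio is then about σ[Φ⁻¹(0.1135) − Φ⁻¹(0.05)] = σ(−1.208 + 1.645) = 0.437σ, so it has no limit.

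**3. Illustration.** There are 750 patients per arm. Day-30 rates are the protocol's 5% and 11.35%. Day-0 and day-90 rates are assumed: 4% and 6% in UC, 9.5% and 12.5% with the OUD-CDS. Expected counts for 000/001/011/111 are 705 / 7.5 / 7.5 / 30 and 656.25 / 8.625 / 13.875 / 71.25. The model has treatment-by-time terms, no clinic effect and exact integration with σ held fixed. The upper bound of the log-likelihood is −558.5.

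| Patient SD | Log-likelihood | Conditional day-30 OR |
|---|---|---|
| 2 | −815.8 | 3.5 |
| 10 | −587.3 | 91 |
| 20 | −566.6 | 6,510 |
| 50 | −559.2 | 2.8 × 10⁹ |

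The reference model using day 30 only gives OR 2.43 and z = 0.889 / 0.203 = 4.37. Over SD 0.5 to 50, z stays at 4.21 to 4.45 and the implied marginal OR at 2.42 to 2.57.

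**4. Same data, SD estimated by common methods.**

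| Method | Patient SD | Day-30 OR | z |
|---|---|---|---|
| PQL | 2.2 | 2.65 | 3.24 |
| Laplace | 132 | 5.9 | 0.66 |
| 7-point adaptive quadrature | 40 | 13.6 | 1.37 |
| 25-point adaptive quadrature | 62 | about 2.5 × 10¹⁷ | – |

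The Laplace fit implies day-30 rates of 40.4% and 40.9%. The maximised values for Laplace (−278.6), 7-point (−495.4) and 25-point (about −520) all lie above the −558.5 bound. These fits are failed approximations, not valid maxima.

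**5. Sensitivity to the assumed rates.** With UC 4.8/5/5.3% and CDS 10.8/11.35/11.6%, z is 3.15 (PQL), 1.00 (Laplace) and 1.02 (7-point), against 4.37. With UC 8.5/10/11.5% and CDS 16.5/18.12/19.5%, z is 3.32, 0.89 and 6.78 (the last with OR about 3 × 10²⁴), against 4.47.

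**6. Clinic intercept added.** In one simulated 30 × 50 data set, the log-likelihood still rises from −1258.9 (SD 1) to −693.9 (SD 80). The OR goes from 1.7 to 1.1 × 10⁹ while z stays at 2.19 to 2.29. In four further simulated trials (ICC 0.03 on the logit scale, an assumption), the joint Laplace fit gives patient SD 127 to 132, OR 4.0 to 15.4 and z 0.48 to 1.08. The day-30 clinic-intercept model gives OR 2.8 to 3.4 and z 3.46 to 5.26.

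**7. The other two readings.** In a joint fit without time terms the SD is finite but extreme (17.6), with OR about 1,450 and z 3.67, and there is no day-30-specific effect. With one day-30 row per patient (no clinic effect), the likelihood is identical at every patient SD, while the conditional OR is 2.43 at SD 0, 10.2 at SD 5 and 85 at SD 10.

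**The case against.** - **The detail may be elsewhere.** Section 13.3 calls itself an overview and defers decisions on the primary analyses to the Statistical Analysis Plan. It names no time term here, although the protocol names a treatment-by-time interaction for Aim 3, costs and safety. Separate day-specific models would also satisfy section 13.4. This stands as a limit: the joint fit is the natural reading, because only the repeatedly recorded outcomes get a patient intercept, but it is not stated. On the one-row reading, however, the patient intercept is redundant and leaves the conditional OR undetermined.
- **The test survives proper integration.** True at a fixed SD: sign, z and implied marginal OR barely move. The harm there is to convergence and to the reported odds ratio.
- **The small z values come from fits that visibly failed.** Also true; comparing fitted with observed rates would expose the Laplace fit. That makes a post hoc change of method likely, which is the reason to settle the model now.
- **The spread between methods is not stable.** On another data set (day-30 rates 10% and 18.12%, one treatment effect across days), Laplace and 5-, 7- and 15-point adaptive quadrature gave OR 1.93 to 2.01 and PQL 2.27, against a crude 1.99. Non-adaptive quadrature ranged from 1.29 to 1.9 × 10⁹. The individual method figures should therefore be read as illustrations only.
- **Other repairs exist.** A marginal model or an ordinal time-to-action model would also work.

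**Conclusion.** The concern holds: no reading makes the patient intercept useful. If days 0, 30 and 90 are fitted jointly with treatment-by-time terms, the absence of a finite maximum follows from the coding and does not depend on the assumed rates. The conditional odds ratio then has no fixed value, and the software's answer depends on the approximation. In the illustration, z ranges from 0.66 to 3.24 across PQL, Laplace and 7-point quadrature, against 4.37 for the day-30 model. Those magnitudes rest on assumed day-0 and day-90 rates, and the four simulated trials on an assumed logit-scale ICC. Without time terms, no day-30 effect is estimated. With one row per patient, the intercept is practically unidentified.

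The sample-size figures are not affected; they already describe a model without a patient intercept. The correction should be made before analysis. If the separate Statistical Analysis Plan already settles these points, section 13.3 still has to agree with it.

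**What to change.** In section 13.3, remove patients from the random-intercept sentence so that all four primary outcomes have a clinic intercept only. State that the primary model for H1.1, H1.2 and H2.1 uses one row per patient, the day-30 status. Analyse days 0 and 90 in separate models of the same form, which keeps the comparisons over time that section 13.4 wants. Bring section 13.1.5, the parallel text in section 2.6 and the separate Statistical Analysis Plan into line, and name the estimation method in that plan.

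The cost is protocol and SAP wording. Data collection, sample size and conduct do not change, and the model then matches the basis on which the trial was powered.

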9.3 Rationale for Site Selection

A total of three study sites involving at least 30 primary care clinics (at least 10 primary care clinics in each healthcare system) will provide for diversity in primary care practices, patient race and ethnicity, geographical distribution, and rural/urban representation.

HealthPartners will serve as Site 1 for this study and served as the sole site for the CTN-0076-Ot pilot study. HealthPartners is the largest consumer-governed nonprofit health care organization in the country, providing care, coverage, research, and education to improve health and well-being in partnership with its members, patients and community. HealthPartners serves more than 1.5 million medical and dental health plan members and more than 1 million patients in its HealthPartners Medical Group (HPMG) and Park Nicollet Medical Group (PNMG) clinics and hospitals. In 2013, HealthPartners and Park Nicollet combined under the name HealthPartners and a single consumer-governed board of directors. The new organization includes a multispecialty group practice of more than 1,700 physicians, seven hospitals, 47 primary care clinics, 22 urgent care locations, 22 dental clinics, and numerous specialty practices in Minnesota and western Wisconsin. The majority of HPMG and PNMG patients (>80%) have commercial health insurance, while approximately 6% are insured via Medicare and 4% via Medicaid. HPMG and PNMG offer outpatient primary and specialty addiction care, day programs, partial hospitalization programs and inpatient treatment for OUD and other substance use disorders. The medical groups refer out for methadone maintenance; for the approximately 40% of patients who are also HealthPartners Insurance members, we will be able to capture data on their methadone prescription dispensings.

The remaining two study sites, Geisinger and Essentia, were selected based on the availability and engagement of an effective clinicians champion, and the care system's ability to: (a) obtain adequate support from their primary care and other care system leadership, (b) modify and install custom EHR code, (c) help determine best ways to integrate the CDS into their clinical workflows and achieve and maintain high clinical use, (d) provide required training for PCPs and staff, and (e) obtain timely IT security clearance and a letter of support from their IT group. These criteria are imperative for ensuring proper functioning and maintenance of the OUD-CDS. They were also

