13.1.4 Randomization and Factors for Stratification

The OUD-CDS software is a system-level intervention comprised of 1) a passively operating web service that gathers, analyzes and retains information pertinent to every web service call, and 2) a user interface that presents a summary of algorithm results to front end users. The web service documents every web service call made by all front-end users in all participating locations so that data pertinent to all targeted visits from all eligible and enrolled patients will be identically collected and available in both treatment arms. The user interface will function as the intervention delivery vehicle and therefore be operative only in intervention locations. Intervention or Control designation will vary randomly by clinic. The OUD-CDS web service will therefore operate

passively in all participating clinics but the user interface will only be turned on in clinics that are randomly assigned to the intervention treatment group.

To the extent that patients tend to receive most of their care over time at a single clinic, and that clinicians tend to practice at a single clinic, it is reasonable to assert that the risk of intervention contamination across clinics is low. However, because it is common for patients to see more than one clinician in a clinic location over time, and for clinicians within a clinic location to discuss aspects of care delivery with each other, the risk of intervention contamination within clinics is rather high. Randomizing by clinic rather than by PCP or patient will minimize risk of intervention contamination.

Generally speaking, randomization should balance treatment groups on factors that enhance or impede intervention uptake and adherence, that are related to and including study outcomes, and on any other unmeasured factors that may affect statistical power. However, the likelihood that factors related to these considerations are balanced may be diminished in cluster-randomized trials due to relatively few randomized units.[33, 34] Covariate constrained randomization will be implemented to balance treatment groups across the study and within health care systems (strata) on factors related to study outcomes, implementation of the intervention, and potential treatment modifiers.

Potential balancing factors include:

- n of waived providers
- n of adult patients at clinic
- % of adult patients with government sponsored insurance
- % of adult patients who are non-Hispanic White

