- % of all patients at high risk for OUD
- % of patients at high risk for OUD provided a with naloxone rescue kit
- % of all patients with diagnosed OUD
- % of all patients with diagnosed OUD with a current MOUD

Each patient will be assigned to the clinic in which his or her first visit that is eligible for the OUD-CDS intervention (i.e., index visit) takes place, and as such will be assigned to the treatment group to which their clinic was randomly assigned. Post-index visits may take place in the same or different clinics or treatment groups relative to the index visit and may or may not be eligible for the OUD-CDS to offer treatment recommendations. In keeping with an intent-to-treat principle, all index and post-index visits and outcome measures for each patient will be attributed to the treatment group assignment of the clinic where the index visit took place.

Further details regarding the randomization procedures including the final balancing factors included in the randomization are provided in a separate study randomization plan.

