13.2 Rationale for Sample Size and Statistical Power

13.2.1 Projected Number of Sites

At least 30 primary care clinics at three participating healthcare systems (i.e., at least 10 primary care clinics per healthcare system) are expected to participate in this study.

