13.2.2 Projected Number of Participants per Site

There must be at least 50 patients with or at high risk for OUD at an index visit at a randomized clinic for it to be included in the analyses. Based on the number of patients with study-eligible visits in the COMPUTE 1.0 pilot study, we expect this will be a low threshold for clinics to attain. The COMPUTE 1.0 intervention was implemented for six months among 55 randomized providers who practiced in 30 clinics. During that time, these providers saw between 14 and 137 patients (provider median = 77; 37-412 patients per clinic, clinic median = 163) who were eligible for the pilot OUD-CDS intervention. To the extent the COMPUTE 2.0 intervention is expected to collect outcome data on patients for 19 to 31 months in the randomized clinics, and study-eligible patients will be seen by all clinic providers, it is plausible to expect that 1,000 study-eligible patients could have index visits at many clinics.

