Hypotheses for Aim 3 predict fewer ED visits (H3.1) and inpatient stays (H3.2) during the observation period of patients receiving care in the OUD-CDS relative to UC clinics. The rate at which each of these outcomes occurs per patient-year will be compared across clinics using generalized estimating equations. Clinic-aggregated counts of ED visits and inpatient stays will be normalized using a Poisson-Normal link function, and the intercept offset by the log of patient-years within the clinic. The model will estimate fixed effects of OUD-CDS, care system and other covariates on the rate of each outcome per patient-year. Should it be feasible, we will also collect and count ED visits and inpatient stays that occurred in the year prior to each patient’s index visit so that treatment group differences in pre-post changes in event rates can be quantified (i.e., treatment by time interaction).

Hypotheses for Aim 4 predict lower healthcare costs and the identification and mitigation of barriers and identification of facilitators to OUD-CDS implementation and uptake. **Analysis of costs** for this aim will include delivery costs of the OUD-CDS and incremental medical care costs attributable to the intervention, defined from the health system perspective. Intervention costs may include resources used for implementation, maintenance, compensation, and PCP and staff training – which may be assessed by interviews/surveys with implementation site staff or study resource use documentation, as appropriate – but will exclude research, development, and measurement costs, using standard micro-cost accounting methods and nationally-representative pricing of inputs. Medical care costs will include all prescribed medications and clinical inpatient, emergency, outpatient, and skilled nursing facility services incurred in the pre- and post-index observation periods by participants in each study group, as indicated by insurance claims and clinical encounter data. The study sample for the cost analysis will be participants who have continuous insurance coverage during the study period, including pharmacy benefits. This sample

will be compared to patients without continuous insurance coverage to assess representativeness and comparative completeness of utilization measurement in comparison to all study participants.

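### The Aim 3 GEE tests of clinic-level counts claim a two-sided 5% error with as few as 30 clinics, but the plan fixes neither a small-sample variance and reference distribution nor the number of covariates

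*Combined protocol and SAP*

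**What the plan says.** Section 13.3 sets the Aim 3 method: "The rate at which each of these outcomes occurs per patient-year will be compared across clinics using generalized estimating equations". ED visits and inpatient stays are summed within clinic, with log patient-years as offset. On model terms it says: "The model will estimate fixed effects of OUD-CDS, care system and other covariates on the rate of each outcome per patient-year". The number and identity of the other covariates are not given.

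Section 13.4 states the error rate: "The event rates in OUD-CDS versus UC clinics will be evaluated using a two-sided test with a Type I error rate of 5" per cent. Section 13.2.1 gives the number of units: "At least 30 primary care clinics at three participating healthcare systems". That is a floor. Section 9.3 describes one system alone as having "seven hospitals, 47 primary care clinics, 22 urgent care locations", so more than 30 may be randomized.

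On allocation, section 13.1.4 says: "Covariate constrained randomization will be implemented to balance treatment groups across the study and within health care systems (strata"). It lists eight potential balancing factors and then adds: "Further details regarding the randomization procedures including the final balancing factors included in the randomization are provided in a separate study randomization plan".

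Section 13.3 describes itself as an overview for primary and secondary outcomes and refers detail to the Statistical Analysis Plan. The extra clarity it promises there concerns the primary outcome analyses. The only robust-variance statements (sections 13.3 and 13.4) concern Aim 4 costs and are not small-sample corrections.

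**The concern.** With one record per clinic, the sample size for the Aim 3 test is the number of clinics. The ordinary GEE test divides the estimate by an uncorrected sandwich standard error and refers the ratio to the normal distribution. That standard error is built from squared residuals, which the fitted model has already shrunk, so with few clinics it tends to be too small. Each further clinic-level covariate shrinks the residuals more.

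The plan recognises few randomized units in sections 10.2 and 13.1.4, but only as a threat to balance. If the default test were used with several clinic-level covariates, a claimed reduction in ED visits or hospitalizations could rest on a test whose real error is two to three times the stated 5%.

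**Working it through.** **1. The nearest figure in the plan.** No power or detectable effect is given for Aim 3, so the check uses Table 3 (section 13.2.2.1), which covers the binary primary outcomes. With k clinics, m patients per clinic, usual-care rate p0 and intervention rate p1:

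p1 − p0 = [t(0.975, k−2) + t(0.80, k−2)] × √{[p0(1−p0) + p1(1−p1)] × [1 + (m−1)ICC] / (mk/2)}

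- k = 30, m = 50, p0 = 5%, ICC = 0.03. The quantiles are 2.048 + 0.855 = 2.903, the design effect is 1 + 49 × 0.03 = 2.47, and mk/2 = 750. The solution is p1 = 11.42%, against 11.35% stated. Normal quantiles give 11.16%.
- k = 10, p0 = 10%. The quantiles are 2.306 + 0.889 = 3.195 and mk/2 = 250. The solution is p1 = 27.02%, against 26.73% stated. Normal quantiles give 24.62%.

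So Table 3 behaves like a t reference on clinics minus 2. The power section appears to allow for few clusters. The Aim 3 test section does not say whether it does.

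**2. Why covariates matter.** The intercept, arm and two system indicators make 4 parameters, and four or eight clinic covariates make 8 or 12. As a rough guide, the uncorrected sandwich is too small by a factor 1 − p/k for p parameters and k clinics. The nominal 1.96 then acts like 1.96 × √(1 − p/k).

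| Clinics | p | p/k | Effective cut-off | Implied two-sided error |
|---|---|---|---|---|
| 30 | 4 | 0.13 | 1.82 | 6.8% |
| 30 | 8 | 0.27 | 1.68 | 9.3% |
| 30 | 12 | 0.40 | 1.52 | 12.9% |
| 60 | 4 | 0.07 | 1.89 | 5.8% |
| 60 | 8 | 0.13 | 1.82 | 6.8% |
| 60 | 12 | 0.20 | 1.75 | 8.0% |

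This ignores the variability of the sandwich and unequal clinics, which push the error up, and constrained allocation, which can pull it down.

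**3. Simulation under no effect.**

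- From the plan: 30 or more clinics in three systems, 1:1 within system, constrained allocation, clinic counts with a log patient-year offset, two-sided 5%.
- Assumed: 0, 4 or 8 clinic covariates (eight being the number of potential balancing factors listed); 300 patient-years per clinic with size CV 0.55 and a floor of 30; 0.8 ED visits per patient-year; between-clinic SD of log rate 0.3; overdispersion 4; allocation drawn from the best 10% of 200; balancing factors explaining 0, 30 or 60% of between-clinic variance; 5,000 replicates per cell.

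Rejection at nominal 5% with the uncorrected sandwich:

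| Clinics, reference | No clinic covariates | Four | Eight |
|---|---|---|---|
| 30, normal | 6.3-10.5% | 10.8-13.8% | 17.8-18.3% |
| 48, normal | 5.0-7.6% | 7.9-9.8% | 12.1-13.5% |
| 60, normal | 4.0-7.8% | 6.7-9.1% | 10.8-11.2% |
| 30, t | 5.0-9.0% | 9.4-11.7% | 15.4-15.6% |

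Repeat runs under the same assumptions agree to within about 1.2 points; the rounded ranges in the verdict cover them. A t reference alone does not repair the test once clinic covariates enter.

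**4. Sensitivity at 30 clinics.** Size CV, between-clinic SD, overdispersion and a hospitalization-like rate of 0.2 were varied. Clinic exposure was also set to 75 or 2,000 patient-years. The lower value is 50 patients × 1.5 years, from section 13.2.2 ("There must be at least 50 patients with or at high risk for OUD at an index visit at a randomized clinic") and the 18 months in section 2.4; the upper is 1,000 patients × about 2 years. Ranges for the normal reference are 4.4-11.8%, 7.9-16.3% and 14.7-20.9%. Under simple rather than constrained allocation the base-case figures are 9.9-10.1%, 14.0-14.4% and 18.6-18.9%. The constraint therefore helps mainly when prognostic factors are left out of the model.

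**5. Remedies at 30 clinics (all covariate counts).**

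- Kauermann-Carroll with t: 2.8-6.9% (2.1-7.7% over sensitivity).
- Average of the Kauermann-Carroll and Mancl-DeRouen standard errors with t: 2.2-5.1% (1.6-5.5%).
- Randomization test within the constrained set: 4.2-5.8% (2,000 replicates).

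**The case against.** The strongest reply is that the harm is hypothetical. Nothing in the plan says an uncorrected sandwich with a normal reference will be used. Variance estimators and covariate lists are ordinary SAP content, and section 13.3 points to an SAP. Table 3 suggests the team thinks in cluster-level degrees of freedom. A model-based variance with a Pearson scale and t would give 3.9-7.8% (2.0-9.3% over sensitivity). This stands in part: the point is conditional, and an SAP cross-reference would close it. But the added clarity section 13.3 promises is for primary outcome analyses, so coverage of Aim 3 is not assured.

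Second, the largest figures depend on assumed covariate counts. That also stands. The eight factors are listed for balancing, and no passage says they enter the Aim 3 model. With arm and system only, and balancing factors that explain 30-60% of between-clinic variance, the base case at 30 clinics is 6.3-8.3%.

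Third, the model itself is ambiguous. Section 13.3 combines GEE with a Poisson-Normal link, which is mixed-model language, and sections 2.6 and 13.1.5 allow either for Aims 1 to 3. If a mixed model is meant, the sandwich figures and correction do not apply. This stands and is part of the fix.

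Fourth, H3.1 and H3.2 are secondary. That limits the consequence, but section 13.4 still claims 5% for them.

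Two stronger readings are tempting. One is that the Aim 3 analysis will be anti-conservative; the documents leave the choice open and do not support that. The other is that the primary analyses are known to be safe, or known to be affected. Section 13.3 gives them mixed models, also with unspecified other covariates and no named reference distribution. They are not assessed here, so neither conclusion follows.

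**Conclusion.** The point holds as a conditional one. As written, the plan does not secure the two-sided 5% it states for H3.1 and H3.2. With the ordinary uncorrected sandwich and normal reference, simulated Type I error is about 5-10%, 11-14% and 18% at 30 clinics with zero, four and eight clinic-level covariates, and about 4-8%, 6-9% and 10-12% at 60. More clinics help, but the covariate count can matter as much.

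The figures rest on assumed event rates, overdispersion, clinic-size spread and covariate counts, and on the model being GEE. Monte Carlo standard error is about 0.3-0.7 points. No error-rate claim is made for the safety comparisons in section 13.9, which state no alpha. This should be fixed; confidence is medium because the SAP was not available.

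**What to change.** In sections 13.3 and 13.4, do the following for Aim 3, or cite the SAP section that already does:

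1. State whether Poisson-Normal means GEE or a mixed model. A mixed model would need a small-sample degrees-of-freedom method or the randomization test below.
2. For GEE, specify either (a) a bias-corrected sandwich (Kauermann-Carroll, or the average of the Kauermann-Carroll and Mancl-DeRouen standard errors) with a t reference on clinics minus model parameters, or (b) a randomization test over the constrained allocation set.
3. Prespecify a short clinic-level covariate list drawn from the final balancing factors.
4. For consistency, use the same method for the other GEE event-rate comparisons (death and overdose in section 13.3.3, safety rates in section 13.9).

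The cost is a few sentences, an option in the analysis code, and wider intervals. At 30 clinics Kauermann-Carroll with t is 1.15, 1.28 and 1.43 times as wide as the uncorrected interval with zero, four and eight covariates; the averaged standard error is 1.21, 1.42 and 1.71 times. At 60 clinics Kauermann-Carroll with t is 1.07, 1.13 and 1.18 times. Both corrections are conservative if strongly prognostic balancing factors are left out (Kauermann-Carroll with t gives 2.1-4.6% when they explain 60%). Kauermann-Carroll with t can still reach 7.7% with eight covariates and very unequal clinics. The randomization test avoids both problems, but the allocation set must be stored and intervals obtained by inversion.
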